Version No:

 2.0 Final

 Date:
 10 March 2023

 EudraCT No:
 2022-003855-32

List of used acronyms and abbreviations

Abbreviation	Term/Explanation
AE	Adverse event = any untoward medical occurrence
CAT	Chronic obstructive disease assessment test
CIOMS	Council for international organizations of medical sciences
CRF	Case report form
CRP	C-reactive protein
СТ	Computer tomography
DSUR	Development safety update report = annual safety report
eGFR	Estimated glomerular filtration rate
EMR	Electronic medical record
EQ5D	A standardized measure of health-related quality of life
EPM	Etikprövningsmyndigheten (English: Swedish Ethical Review Authority)
ESR	Erythrocyte sedimentation rate
ET	Early termination
FSS	Fatigue severity scale
GCP	Good clinical practice
HDPE	High-density polyethylene
HRCT	High resonance computerized tomography
ICD	Informed consent document
ICH	International council for harmonization
IRC	Interim review committee
KI	Karolinska Institutet
KS	Karolinska university hospital
LVFS	Läkemedelsverkets författningssamling (English: Swedish Medical Products Agency's statutes)

 Version No:
 2.0 Final

 Date:
 10 March 2023

 EudraCT No:
 2022-003855-32

MAPS	Malmo POTS score
mMRC	Modified Medical Research Council
MFS	Mental fatigue scale
MIP	Maximal inspiratory pressure
МоСа	Montreal cognitive assessment
MVD	Microvascular dysfunction
MWT	Minute walk test
SAE	Serious adverse event = serious untoward medical occurrence
SAP	Statistical analysis plan
SARS-COV-2	Severe acute respiratory syndrome coronavirus 2
SPC or SmPC	Summary of product characteristics
SUSAR	Suspected unexpected serious adverse reaction
PACS	Post-acute COVID-19 syndrome
PEM	Post exertional malaise
POTS	Postural orthostatic tachycardia syndrome
WHO	World health organization
WOCBP	Woman of childbearing potential

 Version No:
 2.0 Final

 Date:
 10 March 2023

 EudraCT No:
 2022-003855-32

1. Synopsis

EudraCT number: 2022-003855-32

Title: An Interventional, double-Blinded, 2-Arm Study to Investigate the Efficacy of Orally Administered Nirmatrelvir/Ritonavir Compared With Placebo/Ritonavir in

Non-hospitalized Adult Participants suffering from post-COVID

Brief title: PROLIFIC - imPROving quality of LIFe In the long COVID patient

Study code: KI-PROLIFIC-2023

Short There is still a significant unmet need for patients with Post-Acute

background/ COVID syndrome. This study, a 15-day twice daily dosing of

Rationale/Aim: Nirmatrelvir/Ritonavir (300/100 mg) or Placebo/Ritonavir (100mg) will

evaluate the potential ability to provide sustained improvement in quality of life, by using EQ-5D-5L questionnaire, in patients suffering

from post-COVID.

Study objectives and endpoints:	Objectives	Endpoints
	Primary	Primary
	To evaluate the effect of oral administration of nirmatrelvir/ritonavir at Day 16 on quality of life	Change from baseline on the EQ-5D-5L VAS scale at day 16
	Secondary	Secondary
	To evaluate the effect of oral administration of nirmatrelvir/ritonavir in patients with post-COVID-19 symptoms over time on quality of life	Change from baseline on the EQ-5D-5L VAS scale at day 45 and on Day 90
	To evaluate the effect of oral administration of nirmatrelvir/ritonavir on hemodynamic response (only patients diagnosed with POTS)	Change from baseline over time as measured in delta maximum heart rate during active standing test
	To evaluate the effect of oral administration of nirmatrelvir/ritonavir on fever MAPS (only patients diagnosed with POTS)	Change from baseline over time in POTS-specific symptoms as measured by MAPS

 Version No:
 2.0 Final

 Date:
 10 March 2023

 EudraCT No:
 2022-003855-32

	-
To evaluate the effect of oral administration of nirmatrelvir/ritonavir on reactive hyperemia index	Change from baseline endothelial function measured by the EndoPat® device on Day 45
To evaluate the effect of oral administration of nirmatrelvir/ritonavir in 24-h average heart rate	Change from baseline over time in heart rate by ECG monitoring device
To evaluate the effect of oral administration of nirmatrelvir/ritonavir fever	Change from baseline over time in body temperature
To evaluate the effect of oral administration of nirmatrelvir/ritonavir on physical capacity	Change from baseline over time as measured by 6-minute walk test
To evaluate the effect of oral administration of nirmatrelvir/ritonavir on handgrip strength	Change from baseline over time as measured by JAMAR
To evaluate the effect of oral administration of nirmatrelvir/ritonavir on physical activity	Change from baseline over time as measured by accelerometer
To evaluate the effect of oral administration of nirmatrelvir/ritonavir on post exertional malaise	Change from baseline at Day 90 in total score as measured by Post-Exertional Malaise short form
To evaluate the effect of oral administration of nirmatrelvir/ritonavir on fatigue	Change from baseline over time as measured by fatigue severity scale (FSS) and mental fatigue scale (MFS)
To evaluate the effect of oral administration of nirmatrelvir/ritonavir on cognitive dysfunction	Change from baseline over time as measured by MoCA test
To evaluate the effect of oral administration of nirmatrelvir/ritonavir on dyspnea	Change from baseline over time in respiratory symptoms measured by CAT and mMRC
To evaluate the effect of oral administration of	Change from baseline over time in Njimegen questionnaire.

 Version No:
 2.0 Final

 Date:
 10 March 2023

 EudraCT No:
 2022-003855-32

nirmatrelvir/ritonavir on dysfunctional breathing patterns, maximum inspiratory pressure, and lung function	Change from baseline over time in maximal inspiratory pressure (MIP) Change from baseline over time in forced vital capacity (FVC) and forced expiratory volume in one second (FEV1)
To evaluate the effect of oral administration of nirmatrelvir/ritonavir on plasma biomarkers	Change from baseline over time in the following plasma biomarkers: D-dimer, CRP, ESR, ferritin, NTproBNP, LD
To evaluate the effect of oral administration of nirmatrelvir/ritonavir on dysautonomia symptoms	Change from baseline over time as measured by Compass31
Tertiary/Exploratory	Tertiary/Exploratory
To evaluate the effect of oral administration of nirmatrelvir/ritonavir on long-term measurement of breathing pattern	Change from baseline over time in Dynamic spirometry
To evaluate the effect of oral administration of nirmatrelvir/ritonavir on persistence of SARS-CoV-2 virus	 Description at baseline and Day 16 of Protein profiling using Olink Explore Inflammation panel Nucleosome-profiling (using Volition) and circulating spike (using SIMOA™, Quanterix) PBMC profiling for scTCR-sequencing (using BD Rhapsody) with assessment of Super-Ag mediated T-cell activation Assessment of immune system signatures associated with disease states using mRNA-sequencing of stabilized whole blood (PaxGene).
To evaluate the effect of oral administration of nirmatrelvir/ritonavir on changes in immune cell function	Immune cell assessment by high-dimensional cytometry
To evaluate the effect of oral administration of nirmatrelvir/ritonavir on the relationship between genotypes and immune function at the molecular level	Circulating protein levels adjusted for DNA-variants

 Version No:
 2.0 Final

 Date:
 10 March 2023

 EudraCT No:
 2022-003855-32

Study design:	Double-blinded randomized controlled trial		
Study population:	Patients with post-COVID according to WHO definition		
Number of subjects:	400		
Main inclusion criteria:	Patients, ≥18 years of age, diagnosed with post-acute COVID-19 syndrome, with reported EQ-5D-5L VAS<50		
Main exclusion criteria:	Acute COVID-19 infection, other non-related conditions with post- acute COVID-19 syndrome like symptoms, previous treatment with Paxlovid		
Investigational product(s), dosage,	Oral Nirmatrelvir/Ritonavir (Paxlovid®) 300/100 mg twice daily for 15 days		
administration:	Oral Placebo/Ritonavir 100 mg twice daily for 15 days. Randomization 2:1		
Study period:	April 2023 – April 2024		

2. Background and rationale

More than 3 years into the COVID-19 pandemic, there are still significant knowledge gaps within the umbrella definition of Post-Acute COVID-19 syndrome (PACS). Patients with PACS experience a wide variety of symptoms related to physical and cognitive function, including fatigue, dyspnea, "brain fog" or other cognitive symptoms, pain, depression, and gastrointestinal issues which significantly impact quality of life. While conclusive findings based on X-ray and blood sampling may be lacking, measurable deviations such as increased heart rate at rest, oxygen saturation upon physical activity, long-term low-grade temperature are often seen in the PACS patient.

At present there is no curative treatment for PACS at hand. Treatment is focused on symptom management and individualized rehabilitation.

We are proposing an interventional, randomized and placebo-controlled clinical intervention trial of Nirmatrelvir/Ritonavir compared with Placebo/Ritonavir in patients with post-COVID (as defined by WHO) from a database of n=988 post-COVID patients seen at the KI/KS post-COVID clinics since May 2020, and in which extensive clinical and biochemical examinations have been performed. The study will further include deep exploratory investigations of the immune phenotypes in post-COVID patients, including changes upon Nirmatrelvir/Ritonavir (Paxlovid®) treatment at the molecular and cellular level.

 Version No:
 2.0 Final

 Date:
 10 March 2023

 EudraCT No:
 2022-003855-32

2.1. Post-acute COVID-19 syndrome (PACS) and Postural orthostatic tachycardia syndrome (POTS)

Hospitalized patients with severe COVID-19 generally show rapid improvement of the widespread radiological abnormalities seen during the acute phase of COVID-19 pneumonia. However, at six-month follow-up in patients hospitalized för COVID-19 "fibrotic-like" changes have been reported on chest CT. Caruso et al [1] found that 72% of the study participants had signs of "fibrotic-like" changes, whereas only 35% was seen in the study by Han et al [2]. Within the UPPCOV and RECOV research projects [3] of patients with long COVID, many hospitalized patients exhibit residual fibrotic changes as well as bronchiectasis (manuscript in preparation). Restrictive lung function impairment and reduced diffusion capacity is relatively common with prolonged oxygen dependency over time in the most advanced cases. A common finding in the hospitalized patient cohort, and to a lesser extent also in the non-hospitalized cohort, is an uneven parenchymal attenuation in expiratory images with high-resolution computer tomography (HRCT).

Non-hospitalized patients with severe PACS often exhibit dysfunctional breathing patterns with or without hyperventilation triggered by mild/moderate mental and/or physical effort. The level of activity necessary to provoke this abnormal breathing is generally very modest. Moreover, the degree of symptoms varies over time without any obvious triggers. Studies regarding correlation with respiratory symptoms and physiological function as well the pathophysiological mechanism are ongoing as well as rehabilitative interventions. Another frequent objective disease manifestation is post-COVID POTS, which has within our UPPCOV and RECOV research projects mainly been seen in non-hospitalized patients (currently ~200 patients, or 25-30%) (unpublished observation). Unlike classical POTS patients, post-COVID POTS patients often have dyspnea with desaturation upon walking and pulmonary changes (mosaic pattern) in expiratory HRCT imaging suggestive of an overlap among multiple phenotypes. Also, other cardiovascular manifestations e.g., microvascular dysfunction and inappropriate sinus tachycardia, have been diagnosed predominantly in the non-hospitalized cohort.

Fatigue, post-exertional malaise, brain fog, cognitive impairment and breathlessness are common symptoms across all phenotypes and are also commonly reported symptoms reported in other studies [4].

2.2. Post-COVID cohort at the Karolinska University Hospital

The multidisciplinary and multi-professional post-COVID clinic at Karolinska University Hospital assessed its first patient May 11, 2020. To date, more than 1500 patients have been systematically assessed and followed, of which 2/3 have been previously hospitalized with severe COVID-19 and 1/3 were never hospitalized and referred from primary care. Study inclusion is ongoing with 988 patients enrolled as of now (2022-11-18) in the integrated research projects UPPCOV and/or RECOV of which around half were hospitalized. Our cohorts are unique due to a broad and in-depth clinical investigation over time according to our initial hypothesis that long term effects of COVID-19 could possibly be multi-systemic and impact daily function and health related quality of life.

To improve clinical management of the PACS patient, Karolinska University Hospital established in 2020 two post-COVID clinics with specialists in infection, respiratory medicine, cardiology, neurology, renal medicine, psychiatry, psychologists, and physiotherapists, and

 Version No:
 2.0 Final

 Date:
 10 March 2023

 EudraCT No:
 2022-003855-32

developed a tailored battery of clinical examinations for in-depth diagnoses. Patients are followed over time and integrated in the research projects UPPCOV and/or RECOV, which have now included n=988 patients.

Investigating long-term PACS effects and increasing the understanding of the various phenotypes and underlying mechanisms will generate effective ways to inform on novel treatment strategies, develop better protocols for clinical follow-up and design interventions for prevention. Studies and case reports have indicated that viral persistence contributes to PACS and POTS, suggesting that SARS-CoV-2 anti-viral treatment may have beneficial effects in this group of patients [5, 6].

2.3. Previous clinical experience with Paxlovid®

Nirmatrelvir (PF-07321332) is an orally bioavailable Mpro inhibitor of the SARS-CoV-2 Mpro main protease, which is an enzyme that is critical for viral replication and transcription. Nirmatrelvir demonstrated cell culture antiviral activity in a wide range of in-vitro cell cultures but has more importantly demonstrated significant clinical efficacy in the EPIC-HR randomized controlled trial, which enrolled 2,246 adults with laboratory-confirmed diagnosis of mild to moderate SARS-CoV-2 infection within a five-day period and were required to have at least one characteristic or underlying medical condition associated with an increased risk of developing severe illness from COVID-19 [7].

Nirmatrelvir will be co-administered with ritonavir, which is a strong CYP3A4 inhibitor, and is being co-administered with nirmatrelvir to achieve exposures sufficient to suppress viral replication through the entire dosing interval. Ritonavir is not expected to have any antiviral activity against the SARS-CoV-2 virus. However, the present protocol also describes the procedures for managing drugs that may interact with Ritonavir through CYP3A4 or through other cytochrome P450 enzymes, such as CYP2D6, which are described in section 6.3, 7.9 and with references to safety information in Section 9.

The safety and tolerability of nirmatrelvir has been evaluated in over 5,000 participants with acute COVID-19 with risk factors for severe COVID-19 in the EPIC-HR, in a post-exposure prophylaxis study -the 1006 EPIC-PEP trial (NCT05047601), as well as in 1,153 participants with a standard risk profile in the EPIC-SR trial, which was stopped early for futility (NCT05011513). The collective evidence from the trials supports the safety and tolerability profile of a treatment regimen of nirmatrelvir / ritonavir 300/100 mg twice daily for 5 days. Adverse (mostly mild) and serious adverse events were similar in the Paxlovid® and placebo arms of the trials.

The PROLIFIC study will recruit adult patients who were never hospitalized for acute COVID-19, in which the burden of comorbidities and prevalence of chronic medication is lower than in the group of patients suffering from long COVID who were hospitalized in the acute stage. The baseline profile of the subjects should therefore not be dissimilar to EPIC-HR, which justifies keeping the dose at 300/100 mg twice daily as in the acute COVID setting.

The pharmacokinetic profile of nirmatrelvir has been investigated in patients with normal and impaired renal function [8]. In patients with normal renal function or mild impairment, a single dose of 100 mg of nirmatrelvir / ritonavir peaked within 1 hour of administration and was

 Version No:
 2.0 Final

 Date:
 10 March 2023

 EudraCT No:
 2022-003855-32

nearly completely absent in plasma at 24 hours after administration. This suggests that accumulative effects of nirmatrelvir / ritonavir are unlikely. The overall T1/2 was similar in patients with normal and mild renal impairment at ~7 hours. Analysis of urinary excretion data suggests incomplete oral absorption of nirmatrelvir.

Given the differences between acute- and long COVID-19, a prolonged 15 Day treatment period can be motivated by the beneficial observed safety profile of the nirmatrelvir / ritonavir 300/100 mg twice daily dose up to 10 days in safety data [7, 9], and the theoretical need for tissue dissemination of nirmatrelvir / ritonavir to treat potential viral reservoirs.

Hypothesis: Paxlovid® improves health-related quality of life measured with EQ-5D-5L VAS scale vs. placebo/ritonavir in objective and pre-defined clinical phenotypes: POTS, Microvascular dysfunction, inappropriate sinus tachycardia, persistent fever, PEM, fatigue, brain fog, dyspnea, dysfunctional breathing patterns or inflammatory phenotypes (increased D-dimer, CRP, ESR, ferritin)

The purpose of this study is to evaluate the efficacy of nirmatrelvir/ritonavir for the treatment of non-hospitalized patients with post-COVID 19 - a patient group with high unmet medical need. The PROLIFIC study will include non-hospitalized patients only since a) accepted therapies in that group of patients are lacking, b) there are fewer comorbidities, c) there have been indications of persistently ongoing pathology in that patient group, and in some cases viral persistence [5, 6].

3. Benefit-risk evaluation

Specific for this study, there is at present no curative treatment for post-COVID which for the intended study population is a severe condition which affects day to day life with a profound impact on functional capacity and health-related quality of life. It is at present not entirely clear what this condition will contribute to regarding long term organ dysfunction, but several studies indicate long term effects such as the development of diabetes and kidney dysfunction. Any treatment with a curative capacity would be greatly beneficial and outweigh the possible risks.

To summarize nirmatrelvir/ritonavir in the acute COVID patient, the appraisal of the benefit-risk for nirmatrelvir/ritonavir is considered positive for treatment of symptomatic mild-to-moderate COVID-19 in non-hospitalized adult and pediatric patients who are either vaccinated or unvaccinated and at high risk for progression to severe illness, including hospitalization and/or death. An NDA seeking approval for nirmatrelvir/ritonavir 300/100 mg twice daily (q12h) administered orally for 5 days for the treatment in adults and pediatric patients (12 years of age and older weighing at least 40 kg) diagnosed with mild-to-moderate COVID, and who are at high risk for progression to severe COVID-19, including hospitalization or death was submitted in June 2022. The EPIC-PEP trial showed good safety and tolerability measures in up to 10 days of dosing (NCT05047601). The observed benefit-risk profile for nirmatrelvir/ritonavir is also considered favorable for continued study in additional sub-populations of patients who may benefit from treatment with an oral antiviral agent directed against SARS-CoV-2.

 Version No:
 2.0 Final

 Date:
 10 March 2023

 EudraCT No:
 2022-003855-32

Ritonavir in the comparative arm is chosen, as ritonavir may cause adverse effects such as nausea and may thus make it unblind to both study participant and study team. Possible interactions will be considered on an individual level for each patient.

Active standing test: An active standing test will be performed at the baseline visit and on Day 45 and 90 of follow-up. Heart rate (ECG) and blood pressure (Arm-cuff) will be measured after 10 minutes bed rest and for ten minutes standing as well as 5 minutes bed rest after return to supine position. ECG and blood pressure measurements are non-invasive and do not imply any risk for the study subjects. The orthostatic challenge itself is not associated with any foreseeable risk for bodily harm but may be uncomfortable and may produce new or worsening symptoms including lightheadedness, dyspnea, chest pain, syncope, headache, blurred vision, and palpitations. To mitigate the risk for serious symptoms the test will be performed by staff trained in active standing tests and study subjects may abort the test and return to supine position if he or she chooses to.

Endothelial function test: Endothelial function will be measured at baseline and day 45 during follow-up using an EndoPAT® device (Itamar medical). The procedure is non-invasive and takes approximately 20 minutes. After a stabilization period an arm cuff will be inflated to supra systolic pressure for five minutes, The cuff is then deflated, and endothelial function is measured as reactive hyperemia index in the index finger. The procedure is not associated with any foreseeable risk for bodily harm. However, it may be uncomfortable and in rare cases even painful. The procedure will be performed by staff trained in the procedure and the study-subject can opt to abort the measurement at any time.

Physical function tests: 6-minute walk test, maximal inspiratory pressure, hand grip strength, accelerometer (Active PAL) will be performed at baseline, and at Days 16, 45 and 90. The tests are non-invasive and constitute a minimal or no risk of injury and take approximately 30 minutes to perform. The physical tests that will be used are also used in the regular clinical follow-up of long COVID and for other conditions. Participants may experience fatigue during the test session, but the test procedure will be adapted to reduce this risk. The benefits of performing the measurements will outweigh the inconvenience for patients.

Patient reported outcomes: A battery of questionnaires, PRO's, will be distributed to the participants at each visit. As these can be exhausting to fill in, the possibility to bring them home for finalization will be offered, as well as the option to fill in prior to next visit.

Nasal swabs and venipuncture: Nasal swabs for antigen tests, performed at screening and baseline visits, and venipuncture for routine blood sampling as well as research blood samples will be performed at baseline, day 16, 45 and 90. They are standard procedures in routine health care and constitute no risk to the patient but may cause minor pain and discomfort.

In summary, the potential benefits of nirmatrelvir/ritonavir treatment are considered to outweigh the foreseeable risks.

 Version No:
 2.0 Final

 Date:
 10 March 2023

 EudraCT No:
 2022-003855-32

4. Study objectives

4.1. Primary objective

The primary objective of this study is to evaluate the efficacy of twice daily oral administration of nirmatrelvir/ritonavir compared with that of placebo/ritonavir in patients with post-COVID-19 symptoms.

4.2. Description of Objectives, Endpoints and Estimands

The primary, secondary and tertiary/exploratory objectives and endpoints assessed (as described in the schedule of activity) to assess the effect of oral Administration of nirmatrelvir/ritonavir in patients with post-COVID-19 symptoms are summarized in the table below.

Objectives	Endpoints	Estimand
Primary	Primary	Primary
To evaluate the effect of oral administration of nirmatrelvir/ritonavir at Day 16 on quality of life	Change from baseline on the EQ-5D-5L VAS scale at day 16	Estimand 1: This estimand is intended to provide a population-level estimate of the mean treatment effect (nirmatrelvir/ritonavir relative to placebo) on a continuous endpoint over time for all randomized/evaluable participants. The difference of Day 16 on EQ-5D-5L VAS scale between the nirmatrelvir/ritonavir and placebo arms in participants with long COVID estimated with a longitudinal analysis that controls for baseline assessment
Secondary	Secondary	Secondary
To evaluate the effect of oral administration of nirmatrelvir/ritonavir in patients with post-COVID-19 symptoms over time on quality of life	Change from baseline on the EQ-5D-5L VAS scale at day 45 and on Day 90	Estimand 1 (see above)

 Version No:

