5.2. Procedures

5.2.1. Schedule of assessments

Table 1 Schedule of assessments

Visit	Screening	Baseline	Start of Treatment	End of Treatment	Follow-up	Early Termination ^a	Follow-up
Study Day	Day -7 to Day -2	Day -1	Day 1	Day 16	Day 45	Prior to Day 90	Day 90
	Up to 7 days before baseline ^b	± 0 days		± 0 days	± 7 days		± 7 days
Informed consent	Х						
Demography	Х						
Medical history	Х						
Physical examination	Х	Х		Х	Х	Х	X
Vital signs	Х	Х		Х	Х	Х	X
Weight and height ^c	X						
Prior and concomitant therapy	Х	Х		Х	Х	Х	Х
Adjunctive therapeutic procedures	Х	Х		Х	Х	Х	X
Pregnancy test	Х			Х		Х	X
Rapid antigen testing ^d	Х	Χe					
Collect/update secondary contacts ^f		Х		Х	Х		
Randomization		Х					
Physical function tests ⁹	Х	Х		Х	Х		X
Active standing test ^h		Х		Х	Х		
Endothelial Function Test		Х			Х		
Dynamic spirometry		Х		Х	Х		X

Version No: 2.0 Final

Date: 10 March 2023 EudraCT No: 2022-003855-32

Visit	Screening	Baseline	Start of Treatment	End of Treatment	Follow-up	Early Termination ^a	Follow-up
MIP		Х		Х	Х		Х
ECG [†]		Х		Х	Х		Х
CAT ^j		Х		Х	Х		Х
Compass 31 ^j		Х			Х		Х
EQ-5D-5L ^j	Х	Х		Х	Х	Х	Х
FSS ^j		Х		Х	Х		Х
MAPS h, j		Х			Х		Х
MFS ^j		Х		Х	Х		Х
mMRC ^j		X		Х	Х		Х
MoCa ^j		X		Х	Х		Х
Nijmegen ^j		Х		Х	Х		Х
PEM ^j		X					Х
Participant-completed study intervention log			X	X			
Staff review of study diary				Х		Х	
IMP administration			X	X			
PK				Х			
Collection of IMP material (unused IMP, empty blisters, and cans)				Х	[X]	Х	[X]
Hematology, biochemistry, coagulation, and other analyses ^k	Х	Х		Х	Х		Х

Version No: 2.0 Final

Date: 10 March 2023 EudraCT No: 2022-003855-32

Visit	Screening	Baseline	Start of Treatment	End of Treatment	Follow-up	Early Termination ^a	Follow-up
Retained Research Sample for Plasma protein biomarkers		Х		Х	[X]		[X]
Retained Research Sample for Genetics		Х		Х	[X]		[X]
Retained research samples for other biomarkers		Х		Х	[X]		[X]
Adverse events ¹	Х			Х	Х	Х	Х
Long term follow up via EMRs ^m							Х

^a In case of Early Termination of treatment, the assessments should be completed as soon as possible after decision of treatment withdrawal. When possible, all study assessments should continue in accordance with the Schedule of Assessments until completion of the Day 90 visit.

^b Failure to include within 7 days may trigger repeat screening for otherwise eligible patient.

^c Height may be self-reported.

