6.2. Inclusion criteria

To be included in the study, subjects must meet the following criteria:

- 1. The subject has given written consent to participate in the study.
- 2. ≥18 years of age at the time of the Screening Visit
- 3. Post-acute COVID-19 syndrome (PACS) according to the WHO definition
- 4. EQ-5D-5L VAS< 50

 Version No:

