6.4. Screening

Subject eligibility (that subjects fulfill all inclusion criteria and do not meet any exclusion criteria) is established at the screening visit before randomization.

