10.4. Statistical methods

For the primary estimand of the primary endpoint, a linear mixed model (LMM) with subject-specific random intercept will be specified to assess possibles changes over time within and among groups. LMM accounts for both fixed and random effects, can analyze data with repeated measures as well as can handle missing values. Specifically, the LMM will include treatment, time, and time*treatment interaction term as fixed effects, and subject/participant as a random effect. An unstructured correlation matrix will be used. Missing values will be imputed as part of the LMM model assumptions.

No adjustments will be made for multiplicity.

For continuous variables, differences in mean or median between groups will be assessed using Student's t-test (parametric) or Mann-Whitney test (non-parametric) depending on the

 Version No:

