10.5. Sample size calculations

The statistical power to detect a 10-unit placebo/ritonavir adjusted improvement from baseline to Day16 (primary endpoint) was estimated using the following assumptions: a 2:1 case-control ratio, nominal significance of alpha=0.05, 1-tailed test and 90 % power. Based on these assumptions, the study population would need to be at least 207 patients. In the study, ~400 participants will be randomized to a) have at least 207 completers to account for 48% dropouts during the execution of the study and b) increase the statistical power for the secondary endpoints of the study that will only be measured in the subset of patients with POTS, and for the secondary endpoints for which the variabilities in the Swedish post-covid patient population are not well documented.

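### The EQ-5D-5L VAS is recorded at Screening and again on Day -1, but the stated analysis gives the screening value no role; using it as a second covariate is a modest, nearly free gain in precision.

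*Protocol*

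**What the plan says.** - **Two pre-treatment readings.** Section 5.2.1, Table 1, ticks the EQ-5D-5L at Screening (Day -7 to Day -2) and at Baseline (Day -1), then at Days 16, 45 and 90 and at early termination.
- **The screening reading decides entry.** Section 6.2 requires "EQ-5D-5L VAS< 50", and section 6.4 says eligibility "is established at the screening visit before randomization".
- **Primary endpoint and estimand.** Section 4.2 gives the endpoint as "Change from baseline on the EQ-5D-5L VAS scale at day 16", with the arm difference "estimated with a longitudinal analysis that controls for baseline assessment". The wording is singular, and the reading is not named.
- **Model.** Section 10.4 states that "the LMM will include treatment, time, and time*treatment interaction term as fixed effects", with participant as a random effect. For the secondary ANCOVA it names baseline as the covariate. Neither model mentions the screening value.
- **Other endpoints measured at both visits.** Table 1 ticks vital signs, which include body temperature (section 8.5.2), and the row "Hematology, biochemistry, coagulation, and other analyses" at both Screening and Baseline. Temperature and six plasma biomarkers are secondary endpoints. Section 3, however, lists routine blood sampling at baseline and Days 16, 45 and 90 and omits screening.

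**The concern.** The VAS in Appendix A asks about health on the day of completion, so a single reading is an imperfect measure of a patient's usual level. A second reading taken before randomisation can carry information about the Day 16 outcome that the Day -1 reading lacks. Where it does, adjusting for both lowers the residual variance of the treatment contrast. It cannot bias that contrast, because the covariate precedes allocation.

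The protocol pays for this reading and then uses it only to decide entry. What is at stake is some precision on the primary endpoint, and possibly on temperature and the biomarkers.

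**Working it through.** **1. The plan's own sample size.** Section 10.5 gives 2:1 allocation, a one-sided 0.05 test, 90% power, a "10-unit placebo/ritonavir adjusted improvement from baseline to Day16" and 207 patients (138 and 69), but no SD. Solving for the SD:

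SD = 10 × √(69/1.5) / (1.645 + 1.282) = 67.8 / 2.926 = 23.2.

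The dropout step agrees: 207/(1 − 0.48) = 398.1, rounded up to 399, against the stated figure of about 400.

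**2. What a second reading adds, without selection.** Let c be the correlation of Screening with Day -1, b that of Day -1 with Day 16, and s that of Screening with Day 16. None is in the documents, so all are assumed. As a share of the outcome variance, the residual variance is:

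- Day -1 only: 1 − b²
- Both readings: 1 − (b² + s² − 2bsc)/(1 − c²), which is 1 − 2r²/(1 + r) when all three equal r

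| c / b / s | Day -1 only | Both | Reduction |
|---|---|---|---|
| 0.5 / 0.5 / 0.5 | 0.750 | 0.667 | 11% |
| 0.6 / 0.6 / 0.6 | 0.640 | 0.550 | 14% |
| 0.7 / 0.7 / 0.7 | 0.510 | 0.424 | 17% |
| 0.8 / 0.6 / 0.55 | 0.640 | 0.626 | 2.1% |
| 0.8 / 0.6 / 0.50 | 0.640 | 0.639 | 0.2% |

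The gain vanishes as s approaches b × c. In the last row b × c = 0.48 against s = 0.50, so Screening tells almost nothing that Day -1 does not. These unselected figures are the ones that apply to temperature and the biomarkers.

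**3. The VAS after selection below 50.** Eligibility truncates the screening score, which weakens it as a predictor. I simulated trivariate normal scores with unselected mean 40-60 and SD 20 (assumed), kept Screening from 0 to below 50, and regressed Day 16 on Day -1 alone and on both readings.

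| c / b / s | Fall in residual variance |
|---|---|
| 0.5 / 0.5 / 0.5 | about 4-5% |
| 0.6 / 0.6 / 0.6 | about 5-7% |
| 0.7 / 0.7 / 0.7 | about 7-10% |
| 0.8 / 0.6 / 0.55 | about 1% |
| 0.8 / 0.6 / 0.50 | about 0.1% |
| 0.7 / 0.7 / 0.50 | about 0% |

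**4. Effect on power.** Assume that power is 90% when Day -1 alone is adjusted for, that is, that 23.2 is the residual SD of that analysis. Power after a proportional fall f is Φ(2.926/√(1 − f) − 1.645).

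- f = 0: 90.0%
- f = 0.03: 2.926/0.985 = 2.971, giving Φ(1.326) = 90.8%
- f = 0.10: 2.926/0.949 = 3.085, giving Φ(1.440) = 92.5%

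In patients, a 10% fall is worth 400/0.90 − 400 = 44 on 400, and a 1% fall about 4.

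**The case against.** **This belongs in the SAP.** The protocol says its methods are detailed further there, and it never formally defines the baseline value. A reader might infer that the protocol restricts adjustment to one reading. It does not say so: a single Day -1 covariate is the natural reading of section 4.2, not an explicit rule. The protocol is not silent either, because it states the adjustment and lists the model terms, and the screening value appears in neither.

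**A larger mismatch sits beside it.** Section 4.2 promises control for baseline, while section 10.4 lists no baseline covariate. That is a firmer defect but a separate one. Resolving it would still leave the screening reading unused.

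**The gain may be close to nil.** This largely stands. Screening is only one to six days before Day -1, while Day 16 is more than two weeks later, so the two early readings probably correlate more with each other than with the outcome. Section 8.3.1 also lets questionnaires be filled in the day before a visit, which can bring the two readings closer still. The lower end of the range is therefore about zero.

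**Evidence of fluctuation is thin.** Section 2.1 says "the degree of symptoms varies over time without any obvious triggers", but in a paragraph on dysfunctional breathing and about symptoms. It does not establish how much the VAS varies between visits.

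**Screening is selected to be low.** Averaging it into the change score would bring regression to the mean into the within-arm changes. Using it as a covariate avoids this.

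**Conclusion.** The point holds as a modest efficiency gain. The screening VAS is collected before randomisation, should exist for every eligible randomised patient, and has no analytic role in the protocol. After selection below 50, using it would lower residual variance by about 0-10%: 4-10% under equal correlations of 0.5-0.7, and 0-3% if correlation decays with time. Power would move from 90% to about 90-92.5%. These figures rest on assumed correlations, mean and SD, and on the SD of 23.2 implied by 207 patients.

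For temperature and the biomarkers the range is about 0-17%, with 11-17% only under equal correlations. The biomarker case is less secure, because section 3 and Table 1 differ on whether blood is drawn at screening.

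A reader might infer that the primary analysis is biased, or underpowered because of this. The documents support neither. Omitting a pre-randomisation covariate leaves the randomised contrast and its type I error intact, and the loss is small under every pattern examined.

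**What to change.** - In section 4.2 and the primary longitudinal model, keep the Day -1 VAS as baseline for the change score and as a covariate, and add the Screening VAS as a second covariate. Do not average the two.
- State which readings these are. Where a patient is rescreened, use the screening value on which eligibility was settled.
- Optionally do the same for body temperature, and for the plasma biomarkers where a screening sample exists, after reconciling section 3 with Table 1 on screening blood sampling.

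The cost is one degree of freedom per model and a line of text, with no new data or visits. It should be fixed before unblinding.
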